10.3 Handling of Multiplicity

The analyses are for extension phase endpoints only, and will not be controlled for multiplicity.

10.4 Efficacy Subgroup Analysis

No subgroup analyses will be conducted for double-blind extension phase efficacy endpoints.

11.0 Safety Analysis**11.1 General Considerations**

Adverse events (AEs), laboratory data and vital signs are the primary safety parameters in this study. The safety variable will be summarized by treatment according to the treatment a subject actually received.

11.2 Analysis of Adverse Events**11.2.1 Treatment-Emergent Adverse Events**

Treatment-emergent AE for double-blind Extension Phase is defined as any adverse event with an onset date on or after the first dose of double-blind maintenance dose and prior to the open-label dose or up to 30 days after the last dose of double-blind maintenance dose if subject discontinued prematurely in double-blind maintenance phase.

For subjects who entered open-label due to inadequate response, treatment-emergent AEs for open-label Extension Phase will also be summarized by open-label dose. Treatment-emergent AE for open-label Extension Phase is defined as any adverse event with an onset date on or after the first dose of open-label dose and up to 30 days after the last dose of open-label dose.

An overview of treatment-emergent AEs, including AEs of special interest such as adverse events leading to death and adverse events leading to early termination, AEs by

Medical Dictionary for Drug Regulatory Activities (MedDRA version 20.0 or later) preferred term and system organ class, AEs by maximum relationship to study drug, and AEs by maximum severity will be summarized by number and percentage.

Changes in laboratory data will be summarized.

In addition, shift tables and listings will be provided for abnormal values, whereby the normal range of the analyzing laboratory will be used. Vital signs will be analyzed similarly.

The number and percent of subjects experiencing treatment-emergent adverse events will be summarized for the following adverse event categories.

- Any treatment-emergent adverse event.
- Any treatment-emergent adverse event that was rated as possibly related to study drug by the investigator (Reasonable Possibility).
- Any treatment-emergent severe adverse event.
- Any treatment-emergent serious adverse event.
- Any treatment-emergent adverse event leading to discontinuation of study drug.
- Any treatment-emergent adverse event leading to death.
- Any treatment-emergent adverse event of special interest.

Treatment-emergent adverse events will be summarized as follows:

- Grouped by System Organ Class and Preferred Term.
- Grouped by System Organ Class, Preferred Term and Severity.
- Grouped by System Organ Class, Preferred Term and Relationship to Study Drug.
- Grouped by System Organ Class and Preferred Term with subject numbers.

In treatment-emergent AE tables, a subject who reports more than one treatment-emergent AE in different system organ classes will be counted only once in the overall total. A subject who reports two or more different preferred terms which are in the same SOC will be counted only once in the SOC total. A subject who reports more than one treatment AE with the same preferred term will be counted only once for that preferred term using the most extreme incident (i.e., most "severe" for the severity tables and most "related" for the relationship tables).

Adverse events will also be summarized by maximum severity. If a subject has an adverse event with unknown severity, then the subject will be counted in the severity category of "unknown," even if the subject has another occurrence of the same adverse event with a severity present. The only exception is if the subject has another occurrence of the same adverse event with the most extreme severity – "Severe." In this case, the subject will be counted under the "Severe" category.

Adverse events will also be summarized by maximum relationship to study, as assessed by the investigator. If a subject has an adverse event with unknown relationship, then the subject will be counted in the relationship category of "unknown," even if the subject has another occurrence of the same adverse event with a relationship present. The only exception is if the subject has another occurrence of the same adverse event with a relationship assessment of "Reasonable Possibility." In this case, the subject will be counted under the "Reasonable Possibility" category, respectively.

Incidence rates per 100 patient years of exposure to study drug will be presented for AE overviews and for AEs by SOC and preferred term where the number of events will be used as the numerator.

$$100 \times \frac{\text{Number of TEAEs}}{\text{Total Patient Years}}$$

where total patient years is defined as the sum of the study drug exposure of all subjects, as defined in an earlier section, normalized by 365.25, and rounded to 1 decimal place.

Overview of treatment-emergent adverse events and treatment-emergent adverse events during the administration of ABT-494 grouped by System Organ Class and Preferred Term will also be summarized for the Any ABT-494 analysis set by quartile of average daily dose.

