**8.1.5.2        Study Drug Exposure**

Exposure to study drug will be summarized for all subjects who have received at least one dose of study drug. The duration (days) of study drug treatment will be summarized with the mean, standard deviation, median and range for each treatment group. The duration of treatment is defined as the difference between the dates of the first and last doses of the treatment plus 1 day. Study drug compliance of the blinded study drug will be summarized for each treatment group. Compliance is defined as the number of capsules taken (i.e., the difference between the number of capsules dispensed and the number of capsules returned) divided by the number of capsules a subject is supposed to take each day times the length of time that the subject was in the Treatment Phase of the study (i.e., Final/Discontinuation Visit date during Treatment Phase – Day 1 [Baseline] Visit date +1). Subjects with missing data for the number of capsules returned will be excluded from the summary.

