The number and percent of subjects using Crohn's disease specific medications (including corticosteroids, aminosalicylates, immunosuppressants [defined as azathioprine, 6-mercaptopurine, or methotrexate], antibiotics) within past 90 days prior to the Baseline, and at the Baseline will be tabulated. In addition, the number and percent of subjects using Crohn's disease specific immunosuppressants, and biologic therapies at any time prior to Baseline will be tabulated.

8.0**Patient Disposition**

Subject disposition will be presented for subjects in the ITT and safety analysis sets using the following information by treatment group:

- Number and percent of subjects in various analysis sets by treatment group and by investigator and/or site number
- Number and percent of subjects completing extension phase and discontinuing on or before Week 52 visit.
- Subject disposition including the number and percent of subjects who prematurely discontinued the study) by primary reason and by any reason

Summary of protocol deviations will be provided.

9.0**Study Drug Exposure and Compliance**

Study drug exposure and compliance will be summarized using the mean, standard deviation, minimum, median, and maximum. Exposure to study drug will be summarized by separately for double-blind extension phase and open-label extension phase.

Compliance is defined as the number of capsules taken (i.e., the difference between the number of capsules dispensed and the number of capsules returned) divided by the number of capsules a subject is supposed to take each day times the length of time that the subject was in the Treatment Phase of the study (i.e., Final/Discontinuation Visit date during Treatment Phase – Day 1 [Baseline] Visit date + 1). Subjects with missing data for the number of capsules returned will be excluded from the summary.

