11.2 Analysis of Adverse Events

11.2.1 Treatment-Emergent Adverse Events

Treatment-emergent AEs for double-blind Induction period are defined as events that begin or worsen either on or after the first dose of the study medication and within 30 days after the last dose of the study medication for who subjects who discontinued study prior to double-blind Extension Period or up to the first dose of double-blind Extension Period for subjects who received at least a dose of study medication during double-blind extension period. An overview of treatment-emergent AEs, including AEs of special interest such as adverse events leading to death and adverse events leading to early termination, AEs by Medical Dictionary for Drug Regulatory Activities (MedDRA version 18.1 or later) preferred term and system organ class, AEs by maximum relationship to study drug, and AEs by maximum severity will be summarized by number and percentage. Treatment group differences (each ABT-494 dose group versus placebo group, as well as ABT-494 dose groups combined versus placebo group) in the overall incidence of treatment-emergent AEs will be assessed with Fisher's exact test for each preferred term for double-blind induction period.

Changes in laboratory data will be described using statistical characteristics and compared between treatment groups and placebo will be performed using a one-way Analysis of Variance (ANOVA). In addition, shift tables and listings will be provided for abnormal values, whereby the normal range of the analyzing laboratory will be used. Vital signs will be analyzed similarly.

The number and percent of subjects experiencing treatment-emergent adverse events will be summarized for the following adverse event categories. Comparisons of the percent of subjects experiencing an adverse event between treatment groups and placebo will be

performed using Fisher's exact tests. Only P values < 0.100 when rounded to three digits will be presented.

- Any treatment-emergent adverse event.
- Any treatment-emergent adverse event that was rated as possibly related to study drug by the investigator (Reasonable Possibility).
- Any treatment-emergent severe adverse event.
- Any treatment-emergent serious adverse event.
- Any treatment-emergent adverse event leading to discontinuation of study drug.
- Any treatment-emergent adverse event leading to death.
- Any treatment-emergent adverse event of special interest.

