Treatment-emergent adverse events will be summarized as follows:

- Grouped by System Organ Class and Preferred Term.
- A by-subject listing will be provided.
- Grouped by System Organ Class, Preferred Term and Severity.
- Grouped by System Organ Class, Preferred Term and Relationship to Study Drug.
- Grouped by System Organ Class and Preferred Term with subject numbers.

In treatment-emergent AE tables, a subject who reports more than one treatment-emergent AE in different system organ classes will be counted only once in the overall total. A subject who reports two or more different preferred terms which are in the same SOC will be counted only once in the SOC total. A subject who reports more than one treatment AE with the same preferred term will be counted only once for that preferred term using the most extreme incident (i.e., most "severe" for the severity tables and most "related" for the relationship tables).

Adverse events will also be summarized by maximum severity. If a subject has an adverse event with unknown severity, then the subject will be counted in the severity

category of "unknown," even if the subject has another occurrence of the same adverse event with a severity present. The only exception is if the subject has another occurrence of the same adverse event with the most extreme severity – "Severe." In this case, the subject will be counted under the "Severe" category.

Adverse events will also be summarized by maximum relationship to study, as assessed by the investigator. If a subject has an adverse event with unknown relationship, then the subject will be counted in the relationship category of "unknown," even if the subject has another occurrence of the same adverse event with a relationship present. The only exception is if the subject has another occurrence of the same adverse event with a relationship assessment of "Reasonable Possibility." In this case, the subject will be counted under the "Reasonable Possibility" category, respectively.

Incidence rates per 100 patient years of exposure to study drug will be presented for AE overviews and for AEs by SOC and preferred term where the number of events will be used as the numerator.

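### Extension SAP: adverse event rates per 100 patient-years count some events up to 30 days after the last dose but divide by on-drug time only

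*SAP*

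**What the plan says.** **Numerator.** Extension SAP 11.2.1 counts events, not subjects: "where the number of events will be used as the numerator". The window in which an event qualifies depends on how the subject leaves the phase:

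- Double-blind, premature stop: the window runs "up to 30 days after the last dose of double-blind maintenance dose if subject discontinued prematurely in double-blind maintenance phase".
- Double-blind, switch to open label: the window closes at the first open-label dose.
- Open label: the window runs from "on or after the first dose of open-label dose and up to 30 days after the last dose of open-label dose", with no exception.
- Double-blind, completed Week 52: the end of the window is not clearly stated.

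**Denominator.** Section 11.2.1 uses patient-years, "where total patient years is defined as the sum of the study drug exposure of all subjects", and refers back to an earlier section for exposure. That section, 9.0, says "Exposure to study drug will be summarized by separately for double-blind extension phase and open-label extension phase" and defines compliance, but not the duration of exposure. The only definition is in Protocol 8.1.5.2: "The duration of treatment is defined as the difference between the dates of the first and last doses of the treatment plus 1 day". That is on-drug time.

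**Induction SAP.** Section 11.2.1 there also counts events "within 30 days after the last dose of the study medication" for subjects who do not enter the extension, and says "Incidence rates per 100 patient years of exposure to study drug will be presented". It gives no formula for patient-years.

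**The concern.** A rate per unit of time is interpretable when every event counted could have occurred in the time that is counted. Here some events come from days that are missing from the denominator, so the rate is too high relative to a matched calculation.

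The excess does not cancel between groups. The post-dose days attach to subjects who stop early and to open-label subjects, but not to those who switch. If dose groups differ in how subjects leave treatment, part of a difference in rates comes from the counting rule. Rates are planned for the overview tables and by system organ class and preferred term, and adverse events are among the primary safety parameters (Extension SAP 11.1).

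**Working it through.** The documents state no adverse event rate, patient-year total or expected exposure, so there is no planned figure to reproduce. The check derives the size of the mismatch from the written windows.

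**Formula.** Let E be summed exposure days and T summed post-dose days in which events still count.

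- Reported rate / window-matched rate = (events/E) / (events/(E + T)) = 1 + T/E. This needs no assumption about the event rate off drug.
- Reported rate / on-drug rate = 1 + r × T/E, where r is the off-drug event rate divided by the on-drug event rate. The documents do not give r.

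**Inputs from the documents.** Double-blind extension: 36 weeks = 252 days. Open label starts at Week 20 at the earliest, so it lasts at most 52 − 20 = 32 weeks = 224 days. Post-dose window: 30 days for premature double-blind stops, 0 for switchers, 30 for open-label subjects.

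**Assumed inputs.** Shares and timing of stopping and switching are not given. They are varied below.

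**Open-label dose groups, every subject with the full 30 days (1 + 30/E, E = mean days per subject):**

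| Mean exposure (days) | Factor | Factor against on-drug rate, r = 0.5 |
|---|---|---|
| 224 | 1.134 | 1.067 |
| 112 | 1.268 | 1.134 |
| 56 | 1.536 | 1.268 |

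**Double-blind arms, no post-dose days for completers (E and T per subject):**

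- 10% stop at day 126: E = 0.9 × 252 + 0.1 × 126 = 239.4; T = 0.1 × 30 = 3; factor 1.013.
- 20% stop at day 126: E = 0.8 × 252 + 0.2 × 126 = 226.8; T = 6; factor 1.026.
- 40% stop at day 84: E = 0.6 × 252 + 0.4 × 84 = 184.8; T = 12; factor 1.065.
- 40% stop at day 56: E = 0.6 × 252 + 0.4 × 56 = 173.6; T = 12; factor 1.069.

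If completers also carried 30 days, T would be 30 in each case, and the first three factors would become 1.125, 1.132 and 1.162. The open question about completers therefore matters more than the stopping pattern.

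**Does shorter exposure always mean more excess?** Take an arm in which 50% switch at day 42, 5% stop at day 126 and 45% complete. E = 0.45 × 252 + 0.5 × 42 + 0.05 × 126 = 140.7; T = 0.05 × 30 = 1.5; factor 1.011. The 20% arm above has the longer mean exposure (226.8 days) and the larger factor (1.026). With post-dose days for completers the order is the same (1.107 against 1.132).

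**The case against.** Several points on the other side have force.

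- **The rate is openly labelled as per exposure to study drug.** Subject counts and percentages are tabulated beside it and do not depend on the denominator. The Extension SAP plans no test of rates between arms. All true, and it limits the harm. A label does not, however, supply the missing days.
- **A reader might infer that every short-exposure group is inflated most.** The documents do not support that. Switching for inadequate response is a designed route to short double-blind exposure, and it adds no post-dose days.
- **A reader might infer 30/252 = 12% for a subject with the full 36 weeks.** No subject with a clearly written 30-day window has 252 days: double-blind completers did not stop prematurely, and open label lasts at most 224 days.
- **A reader might quote 30/28 = 107%.** That describes one subject with four weeks of treatment. It would describe a dose group only if mean exposure were that short, and nothing in the documents says so.
- **Open-label completers may not carry the full window.** Under Protocol 5.1, those who enter Study M14-327 have no 30-day follow-up visit here, and Week 52 becomes Week 0 of that study. The open-label figures are upper values to that extent.
- **Off-drug time is not on-drug time.** Protocol 3.0 gives an elimination half-life of about 8 to 16 hours, so most of the 30 days is off drug. Adding it to the denominator changes what the rate describes. This is a reason to offer a second remedy, not to leave the windows unequal.
- **The Induction SAP is weaker ground.** It gives no denominator formula, subjects who enter the extension carry no post-dose days, and Extension SAP 3.0 says that analysis was already performed.

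**Conclusion.** The mismatch in the Extension SAP stands, and its direction is upward wherever any subject has counted post-dose days. Its size follows T/E.

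- Double-blind arms: about 1-7%, on assumed stopping shares and times and with no post-dose days for completers.
- Open-label dose groups: about 13% at 224 days to 54% at 56 days if all subjects carry the full 30 days; less with rollover.

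These compare the reported rate with a window-matched one. As an excess over the on-drug rate they assume equal event rates on and off drug; at half the rate off drug, the excess halves. The point concerns exposure-adjusted rates only and is worth correcting because it varies with how subjects leave treatment.

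**What to change.** In the Extension SAP:

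1. Define exposure duration in 9.0, so that the reference in 11.2.1 leads to a definition.
2. State where the treatment-emergent window ends for double-blind subjects who complete Week 52.
3. Use one window for events and time, in one of two ways:
   - time at risk as denominator, from the first dose of the phase to the earliest of last dose + 30 days, first dose of the next phase or study, or last contact; or
   - on-drug exposure as denominator, with only on-drug events in the rate numerator.

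The cost is a few sentences and one derived variable. Rates become slightly lower. The first option includes off-drug days in the denominator; the second leaves post-dose events out of the rates, though they stay in the counts and percentages. Re-running the completed Induction rates is optional.

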4.2 Design Diagram

[figure not shown]
This is a Phase 2, multicenter, randomized, double-blind, placebo-controlled study designed to evaluate the efficacy, safety, and pharmacokinetics of ABT-494 as induction

therapy in subjects with moderately to severely active Crohn's disease and evidence of mucosal inflammation defined by a SES-CD ≥ 6 (or ≥ 4 for subjects with disease limited to the ileum) and average daily soft/liquid stool frequency ≥ 2.5 or average daily abdominal pain score of ≥ 2.0 ; and CDAI ≥ 220 and ≤ 450 , with a history of inadequate response or intolerance to immunomodulators and/or anti-TNF therapy. The study will allow enrollment of up to 30% of subjects who were primary non responders to anti-TNF treatment.

The study is designed to enroll approximately 210 subjects to meet scientific and regulatory objectives without enrolling an undue number of subjects in alignment with ethical considerations. Therefore, if the target numbers of subjects have been enrolled, there is a possibility that additional subjects in screening will not be enrolled.

The study duration could be up to 60 weeks, including a Screening Period of up to 35 days, a 16-week double-blind induction period, a 36-week double-blind extension phase, and a 30-day follow-up period. Subjects who met eligibility criteria were randomized in a 1:1:1:1:1:1 ratio to one of the double-blinded induction treatment arms.

[figure not shown]
The schematics of the overall study design are shown in [Figure 1](#) and [Figure 2](#).

Figure 1. Study Design Schematic

*The 6 mg BID dose arm was added to replace the 24 mg QD dose arm in Protocol Amendment 2

**Subjects who were re-randomized at Week 16 to 24 mg QD prior to Protocol Amendment 2 will continue to receive the double-blind 24 mg QD dose until Week 52/PD.

Figure 2. Study Design Schematic for Open-Label Extension Option for Patients Who Do Not Adequately Respond During the Extension Phase

Screening Period

Within 35 days prior to the Baseline Visit, subjects received a full explanation of the study design and study procedures, provided a written informed consent, and underwent the screening procedures as outlined in [Table 1](#).

An e-diary was dispensed and training were provided to the subject at the Screening Visit.

Laboratory tests performed during the Screening period can be repeated in case the abnormalities are considered to be transient by the investigator.

16-Week Induction Period

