This period began at the Baseline Visit (Week 0) and end at the Week 16 Visit. At the Baseline Visit, subjects who met all the inclusion criteria and none of the exclusion criteria described in the protocol (Section 5.2.1 and Section 5.2.2) were enrolled into the study and randomized to double-blind induction period. The randomization at Baseline

were stratified by endoscopic disease severity (SES-CD < 15 and \geq 15), prior anti-TNF use (naïve and experienced), and by participation in the substudy of the gene expression in intestinal biopsies (Yes and No). As part of the randomization at Baseline, subjects were randomly assigned (1:1) to have their follow-up ileocolonoscopy done at Week 12 or Week 16. During this period of the study, subjects visited the study site at Weeks 2, 4, 8, 12 and 16. A \pm 3-day window is permitted around scheduled study visits. The last dose of study drug during this period is taken the evening prior to the Week 16 visit.

However, the stratification factor Prior anti-TNF use (naïve and experienced) was added under Amendment 3, and there are less than 10 anti-TNF naïve subjects enrolled under Amendment 3. Therefore, the Prior anti-TNF use will not be included in all analysis as a stratification factor.

Subjects may discontinue study drug treatment at any time during study participation. Subjects that end study participation early will have an Early Termination (ET) Visit and complete the procedures outlined for the ET Visit in [Table 1](#) as soon as possible after the last dose of study drug and preferably prior to the administration of any new therapies.

36-Week Extension Phase

At Week 16, subjects who have completed the induction period will be re-randomized in a ratio of 1:1:1 to one of the three double-blinded doses of ABT-494 3 mg BID, 6 mg BID or 12 mg BID. The re-randomization will be stratified by dose received during the first 16 weeks, and overall response (responder versus non-responder) at Week 16. The subjects who were re-randomized at Week 16 to ABT-494 24 mg QD prior to Protocol Amendment 2 will continue to receive the same double-blind dose until Week 52/PD.

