5.0 Analysis Populations

5.1 Definition for Analysis Populations

The intent-to-treat responders (ITT-R) and intent-to-treat non-responders (ITT-NR) analysis sets includes all re-randomized subjects in the double-blind extension phase and are responders and non-responders at Week 16, respectively.

For the ITT-R and ITT-NR analysis sets, subjects are assigned to a treatment group based on the re-randomization schedule, regardless of the treatment actually received. The ITT-R and ITT-NR analysis sets will be used as primary sets for all efficacy analysis. Subjects who were randomized to placebo during the Induction Period will be summarized separately.

The intent-to-treat clinical responders (ITT-CR) and intent-to-treat clinical non-responders (ITT-CNR) analysis sets includes all re-randomized subjects in the double-blind extension phase and are clinical responders and clinical non-responders at Week 16, respectively.

For the ITT-CR and ITT-CNR analysis sets, subjects are assigned to a treatment group based on the re-randomization schedule, regardless of the treatment actually received. The ITT-CR and ITT-CNR analysis sets will be used for sensitivity analysis. Subjects who were randomized to placebo during the Induction Period will be summarized separately.

The safety analysis set consists of all subjects who received at least one dose of study medication in the Extension Phase. For the safety analysis sets, subjects are assigned to a treatment group based on the treatment actually received, regardless the treatment randomized. The safety analysis set will be used for all safety analysis of Extension phase.

Any ABT-494 analysis set will consist of all subjects who received at least one dose of ABT-494 during Induction or Extension. Any ABT-494 analysis set will be used for cumulative safety analysis (from Induction baseline to study end).

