5.2 Variables Used for Stratification of Randomization

At Baseline, subjects were randomized in a 1:1:1:1:1:1 ratio to receive one of the six treatment groups (double-blind ABT-494 induction doses or matching placebo).

The following are the treatment groups:

Group 1: ABT-494 3 mg BID

Group 2: ABT-494 6 mg BID

Group 3: ABT-494 12 mg BID

Group 4: ABT-494 24 mg BID

Group 5: ABT-494 24 mg QD

Group 6: Placebo

The randomization at Baseline was stratified by endoscopic disease severity (SES-CD < 15 and \geq 15), prior anti-TNF use (naïve and experienced), and by participation in the substudy of the gene expression in intestinal biopsies (Yes and No). As part of the randomization at Baseline, subjects were randomly assigned (1:1) to have their follow-up ileocolonoscopy done at Week 12 or Week 16.

At Week 16, subjects who have completed the induction period were re-randomized in a ratio of 1:1:1 to one of the three double-blinded doses of ABT-494 3 mg BID, 6 mg BID or 12 mg BID. The re-randomization was stratified by dose received during the first 16 weeks, and overall response (responder versus non-responder) at Week 16. The subjects who were re-randomized at Week 16 to ABT-494 24 mg QD prior to Protocol Amendment 2 continued to receive the same double-blind dose until Week 52/PD.

Overall response consists of both Endoscopic response and Clinical response. The central reader endoscopic score will be used for calculating the Endoscopic response for the evaluation of the efficacy endpoints. However, for stratification re-randomization, the endoscopic score at baseline from central reader and the endoscopic score at Week 12 or Week 16 from site local reader will be used in order to determine response status.

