11.3 Analysis of Laboratory Data

Changes from Induction Baseline during Extension in continuous laboratory parameters will be summarized by n, mean, standard deviation, and median value value for each treatment group.

Cross (Shift) tables from Induction Baseline to the final value according to the normal range will be provided for each hematology, clinical chemistry parameter and urinalysis parameter except for the microscopic examination.

For selected laboratory parameter with Common Toxicity Criteria (CTC) a listing of all subjects with any laboratory determinations meeting CTC Version 4.03 (or later) of Grade ≥ 3 will be provided. For hemoglobin, an additional list will also be provided based on CTC Version 3.0 (or later) of Grade ≥ 2 . For each of these subjects, the whole course of the parameter will be listed. For subjects with laboratory values with CTC ≥ 3 , all of the laboratory parameters for those subjects will be listed. For subjects with laboratory values with CTC 4, all of the laboratory parameters for those subjects will be listed.

For subjects who switched op open-label therapy, the above tables will also be presented by the open-label dose.

In addition, Cross (Shift) tables from Induction Baseline to the final value according to the normal range will be provided for each hematology, clinical chemistry parameter and urinalysis parameter except for the microscopic examination for the Any ABT-494 analysis set by quartile of average daily dose.

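### Cumulative safety grouped only by quartile of average daily dose can show a dose pattern that rescue and stopping produce; split it by period and dose at onset

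*SAP*

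**What the plan says.** Extension SAP 5.1 defines the population: "Any ABT-494 analysis set will consist of all subjects who received at least one dose of ABT-494 during Induction or Extension". It assigns this set to cumulative safety, from induction baseline to study end.

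Two displays use it. In 11.2.1, the AE overview and the AEs by system organ class and preferred term "will also be summarized for the Any ABT-494 analysis set by quartile of average daily dose". In 11.3, the shift tables are repeated "for the Any ABT-494 analysis set by quartile of average daily dose". No test is attached to either. Average daily dose, its denominator, the handling of interruptions and the quartile cut-points are not defined, and no caveat is given.

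Dose can change several times. After induction, subjects are "re-randomized in a ratio of 1:1:1 to one of the three double-blinded doses of ABT-494 3 mg BID", 6 mg BID or 12 mg BID. From Week 20, inadequate responders may move to open-label 12 mg BID and, if still inadequate after four weeks, to 24 mg BID (Extension SAP 4.2). AEs may lead to de-escalation (same section) or withdrawal (Protocol 5.4.1).

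Other AE tables are organised by dose within a period:
- induction, by dose against placebo (Induction SAP 11.2.1);
- double-blind extension, by treatment received and ending at the first open-label dose (Extension SAP 11.1 and 11.2.1);
- open label, by open-label dose (Extension SAP 11.2.1).

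**The concern.** A subject's average daily dose is known only when treatment ends, so an AE in Week 6 is filed under a value that depends on later dosing. Two routes link that value to the outcome. An AE that stops drug freezes the average at the doses taken so far. Rescue for active disease raises the average, and active disease may itself generate AEs.

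The study is meant to define the dose-response profile (Protocol 5.6.3) and to inform Phase 3 dose selection (Induction SAP 10.1). A cumulative safety table ordered by dose quartile is likely to be read as dose-toxicity evidence, and the SAP says nothing to discourage that.

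**Working it through.** The plan states no figure for this analysis, so there is none to reproduce.

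**Inputs from the documents.** Induction: "subjects were randomized in a 1:1:1:1:1:1 ratio to receive one of the six treatment groups", with total daily doses of 6, 12, 24, 48, 24 (QD) and 0 mg. Periods: "a 16-week double-blind induction period, a 36-week double-blind extension phase". Extension doses: 6, 12 or 24 mg/day. Rescue: 24, then 48 mg/day.

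**Assumed definition.** Average daily dose = sum of (daily dose × weeks on it) ÷ weeks of ABT-494 exposure.

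**Dosing paths (mg/day)**

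| Path | Calculation | Average |
|---|---|---|
| 3 mg BID in both periods, no rescue | 6 throughout | 6.0 |
| Same, one step at Week 36 | (6×36 + 24×16)/52 | 11.5 |
| Same, one step at Week 20 | (6×20 + 24×32)/52 | 17.1 |
| Same, steps at Weeks 36 and 40 | (6×36 + 24×4 + 48×12)/52 | 17.1 |
| Same, steps at Weeks 20 and 24 | (6×20 + 24×4 + 48×28)/52 | 30.0 |
| Placebo then 3 mg BID, steps at Weeks 20 and 24 | (6×4 + 24×4 + 48×28)/36 | 40.7 |
| 24 mg BID then 12 mg BID, no rescue | (48×16 + 24×36)/52 | 31.4 |

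The same randomised assignments (3 mg BID twice) span 6.0 to 30.0, so rescue can carry a subject from the bottom of the range to near the highest unrescued completer value, 31.4. An average of 48 occurs only in subjects on 24 mg BID who stop before any extension dose.

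**The denominator matters.** A 24 mg BID subject who stops at Week 8 averages 48 over exposure weeks, but 48×8/52 = 7.4 if the divisor is the planned 52 weeks. The undefined choice moves that subject from the top group to the bottom.

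**Simulation with no dose effect.** All runs use the documented arms and re-randomisation; rates are events per 100 patient-years (PY). The following are assumptions, not in the documents:
- Rows 1-7: true rate 200 per 100 PY. Rows with rescue have 40% inadequate responders, rescued at Week 20, 28 or 36. Linked rows add log-normal, disease-linked AE heterogeneity. Rows 6-7 add disease-linked dropout of 0.2 per year and a 3% or 10% chance of stopping in a week with an AE.
- Rows 8-9: constant hazard, and every event stops drug (true rate 15.7).
- Rows 10-11: 30% escalated, unrelated to AEs.

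| Row | Mechanism | Q1 | Q2 | Q3 | Q4 | Q4/Q1 |
|---|---|---|---|---|---|---|
| 1 | Re-randomisation only (log-SD 0.5) | 200 | 200 | 200 | 201 | 1.00 |
| 2 | Rescue unrelated to AEs | 200 | 200 | 200 | 200 | 1.00 |
| 3 | Rescue linked, log-SD 0.3 | 173 | 184 | 202 | 243 | 1.40 |
| 4 | Rescue linked, log-SD 0.5 | 154 | 173 | 203 | 274 | 1.78 |
| 5 | Rescue linked, log-SD 0.7 | 135 | 162 | 204 | 303 | 2.24 |
| 6 | Linked (0.5), 3% stopping | 158 | 170 | 185 | 259 | 1.64 |
| 7 | Linked (0.5), 10% stopping | 161 | 167 | 189 | 247 | 1.53 |
| 8 | Every event stops drug, no rescue | 10.8 | 15.0 | 11.5 | 27.6 | 2.56 |
| 9 | Every event stops drug, 20% escalated | 11.8 | 16.0 | 20.8 | 14.9 | 1.26 |
| 10 | 10% of AEs stop drug | 156 | 151 | 158 | 150 | 0.96 |
| 11 | 5% of AEs stop drug | 154 | 153 | 156 | 151 | 0.98 |

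Stopping alone, at 3-10% per AE week, gives Q4/Q1 of 1.03 to 1.20. Many subjects share an identical average, so tie handling matters: changing only the tie rule turns row 9 into 17.8, 13.8, 9.1, 18.8.

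**Checking the alternative.** In the row 8 setting, dose at onset gives 15.5-16.2 in every group. Pooling dose at onset over the whole study can still mislead. With the hazard doubled in Weeks 0-16 and no rescue or stopping, the quartile table reads 130, 129, 134, 128, while pooled dose at onset reads 121, 121, 134, 207 for 6, 12, 24 and 48 mg/day. The reason is that 24 mg BID is taken only in induction or after rescue. In a disease-linked rescue run where quartile rates ranged from 105 to 199, dose at onset within induction alone was flat at 148-151.

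**The case against.** The best defence is that safety by dose is already covered. Each period has AE tables by treatment, the double-blind window closes at the first open-label dose, and rates per patient-year are planned. The quartile table is an untested extra. This stands: a reader might infer that the plan offers no sound view of safety by dose, and the documents do not support that. What they lack is a display of the cumulative set that respects those periods.

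A reader might also infer that the quartile table will manufacture a dose-toxicity gradient. That is too strong. Rows 10 and 11 are almost flat, row 9 is not monotone, and direction changes with the rescue share and the tie rule. Nor does re-randomisation bias the table by itself: it is random within strata ("The re-randomization will be stratified by dose received during the first 16 weeks, and overall response (responder versus non-responder) at Week 16") and only blends doses.

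The assumption that every event stops drug is extreme for AEs in general, since Protocol 5.4.1 withdraws subjects only for events that rule out continuing. It is exact, however, for one row of the overview being split, AEs leading to discontinuation. The 30.0 mg/day path is also extreme: it needs both steps at the earliest times, and Week 24 has no scheduled visit. Later or single steps give 11.5 to 17.1.

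**Conclusion.** The concern holds in a limited form. The only grouping specified for the cumulative safety set depends partly on what happens after the event, is undefined, and carries no warning. With no dose effect it can show a pattern, chiefly for AEs leading to discontinuation (10.8 to 27.6 against a true 15.7) and where AEs track the disease activity that triggers rescue (Q4/Q1 of 1.40 to 2.24). It can also inflate a real effect: a 1.35-fold increase from 6 to 48 mg/day shows as 1.18 without these mechanisms and 1.87 with them. Where few AEs stop drug and AEs are unrelated to rescue, the distortion is small.

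The path arithmetic rests on documented doses and durations plus the assumed denominator. The simulated sizes and directions rest on the AE rate, rescue share, stopping probability and disease link, none of which the documents give. This is a cheap improvement to a descriptive table and does not affect any efficacy conclusion.

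**What to change.** For the Any ABT-494 set, tabulate events and patient-years by the ABT-494 dose being taken at onset, split into induction, double-blind extension and open label. Summarise laboratory values by the dose at the time of the value, with the same split. Do not pool dose at onset across periods without that split.

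Keep the quartile tables only as a supplement. Define average daily dose (numerator, denominator, interruptions), the cut-points and the tie rule. State that neither the quartile tables nor the open-label rows are dose-response evidence, and refer readers to the randomised-period summaries.

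The cost is a little programming with dosing dates already collected; no new data are needed. One limit remains: the open-label rows stay confounded by non-response, because subjects reach those doses through inadequate response.
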